## 9.0 Statistical Considerations

Five sets of data will be collected from each of the devices and statistical mean and standard error of deviation from the mean will calculated.

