Statistical Analysis Plan

Protocol Title

Measurement of Oxygen Saturation in healthy human volunteers before, during and after hyperemic events using Multi-Modal Techniques: Spatial Frequency Domain Imaging (SFDI), transcutaneous oxygen measurement (TCOM), Pulse Oximeter, and Apple Watch.

Principal Investigator:

[name]. Assistant Professor, Indiana Center for Regenerative Medicine and Engineering at Indiana University Department of Surgery, Division of Plastic Surgery School of Medicine, Indiana University Analysis will be performed based on search of answers for the questions designed.

Q1: What are the correlations between the measurements we've taken? Are those correlations significant?

The repeated measures correlations for the measurements. Use repeated measures correlation because we have repeated measures for our data (we get values for each measurement four separate times).

Q2: What are the differences between males' and females' measurements, over time?

We have 20 subjects (13 male, 7 female). We have 5 parameters for each subject: StO2, HbO2, HbR, HbT1, and HBT2. Each measurement will be recorded at 4 time points: baseline, occlusion, reactive hyperemia, and recovery. Plots showing how subjects' measurements changed over time will be obtained. The mean measurement value for males and females, over time will be obtained. Hypothesized that males' and females' measurements follow similar patterns over time. StO2 for males will have higher average HbO2, HbR, HbT1 and HbT2 measurements than females, over all time points compared to females.

Q3. Is this male/female gap in measurements statistically significant, though?

To answer this, I fit multivariate linear regression models at each time point. Results of multivariate linear regression models, for each time point will be obtained. Multivariate models are basically just regression models with multiple outcome variables; in this case, the outcomes are the 5 measurements. The regression coefficients for the intercepts are basically the estimated average measurement for males, for that measurement, at that time point; the p values for the intercepts don't really matter. The regression coefficients for female is just the estimated average difference between males and females, for that measurement, at that time point.

Example:

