For StO2 at time 1, it's estimated that males have an StO2 value of 62, with a 95% confidence interval of 54 to 70. It's estimated that females have StO2 values at time 1 that are 4 higher than males, on average [95% confidence interval ranges from 11 lower than males, to 19 higher than males]. That confidence interval [-11 to 19] contains 0, so there's a strong enough possibility that the difference between male and female StO2 values at time 1 is 0 (i.e. there's no difference). Because of that, the p value for Time 1/StO2/Female is 0.581, which is greater than .05, which

means we can't reject the idea the females and males have the same StO2 values at time 1.

Q2: Instead of gender, what about differences between skin type (II and III vs. IV)?

Plot of measurements over time for subjects with skin type II and III vs. skin type IV will be analyzed. The data represent the mean measurement value for skin types 2 and 3 vs skin type 4, over time. Based on the above plots, it appears that (on average) those with skin type 4 have lower StO2 and HbO2 over time, compared to those with skin type 2 and 3. Skin type 4s appear to have higher HbR and HbT1 over time, compared to skin type II and III. There's a lot of variation in HBT2 over time, and both skin type groups have similar mean values over time. Like for gender, I fit separate multivariate linear regression models for each time point. The regression coefficients for the intercepts are basically the estimated average measurement for the skin type II + III group, for that measurement, at that time point; the p values for the intercepts don't really matter. The regression coefficients for skin type IV is just the estimated average difference between 4s and 2s + 3s, for that measurement, at that time point.

Example:

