For StO2 at time 1, it's estimated that type 2s and 3s have an StO2 value of 71, with a 95% confidence interval of 63 to 78. It's estimated that type 4s have StO2 values at time 1 that are 20 lower than type 2s and 3s, on average [95% confidence interval ranges from 33 lower than 2s and 3s, to 7 lower than 2s and 3s]. That confidence interval [-33 to -7] does not contain 0, meaning we're confident that the difference between 4s and 2s/3s is not 0. Because of that, the p value for Time 1/StO2/Female is 0.004, which is less than .05, which means we can reject the idea that 4s and 2s/3s have the same StO2 values at time 1. Most of the 5 measurements are correlated with one another. Females and males had similar measurements at baseline, but started to differ in HbO2, HbR, HbT1, and HbT2 from inflation onwards. Those with skin type 4 had lower StO2, higher HbR, and higher HbT1 compared to those with skin type 2 and 3, at all-time points; the two groups didn't significantly differ in regard to HbO2 and HbT2 at any time.

Abbreviation StO2= tissue oxygen saturation HbO2=oxy hemoglobin HbR= deoxy hemoglobin HbT1= superficial perfusion hemoglobin HbT2= deep perfusion hemoglobin TCOM=trans-cutaneous oxygen measurement

SFDI=spatial frequency domain imaging

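### The SAP's statement that a sex difference started at inflation is untested: no planned analysis puts an interval or a test on a change in the sex gap, and baseline similarity is not demonstrated

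*SAP*

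**What the plan says.** The SAP's second question (Q2) asks how males and females differ over time. It gives the sample ("We have 20 subjects (13 male, 7 female") and the schedule: "Each measurement will be recorded at 4 time points: baseline, occlusion, reactive hyperemia, and recovery". It plans plots and group means over time, and hypothesises that the sexes' "measurements follow similar patterns over time".

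Q3 asks whether the gap is statistically significant. The method is: "I fit multivariate linear regression models at each time point". The SAP defines what that model estimates: "The regression coefficients for female is just the estimated average difference between males and females, for that measurement, at that time point". The worked example is StO2 at baseline: females 4 higher, 95% CI -11 to 19, p = 0.581. The SAP reads it correctly, saying the result "means we can't reject the idea the females and males have the same StO2 values at time 1".

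The only method that uses the repeated measurements jointly is the Q1 repeated measures correlation between parameters, which is described without a sex term. Protocol section 9.0 adds only that "statistical mean and standard error of deviation from the mean will calculated".

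The closing summary then concludes: "Females and males had similar measurements at baseline, but started to differ in HbO2, HbR, HbT1, and HbT2 from inflation onwards".

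**The concern.** The summary sentence makes two claims. One is that the sexes were alike at baseline. The other is that a difference in four measures arose once the cuff was inflated. The second claim concerns how the sex gap moves over time. A set of separate models, one per time point, says whether a gap is detectable at each time. A non-significant result followed by a significant one is not evidence that the gap changed, because the two estimates may differ by no more than chance.

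The sentence can be read as a sex-specific response to occlusion, which would be a physiological finding. The SAP's own Q2 is about differences over time, so the question is one the plan raises and then does not analyse inferentially. For baseline, failure to detect a gap with 7 females says little about how small the gap is.

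**Working it through.** **Inputs from the SAP.** 13 males and 7 females, so 13 + 7 - 2 = 18 residual df; four time points; five measures; StO2 baseline gap +4, 95% CI -11 to 19, p = 0.581.

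**Inputs assumed.** Equal SDs in the two sexes and over time; true gaps of 0.8 and 1.0 SD; correlation rho between baseline and a later time of 0.3 to 0.8. The documents give neither rho nor any estimate for HbO2, HbR, HbT1 or HbT2.

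**1. The plan's own figure.** Half-width 15; t(0.975, 18) = 2.101. SE = 15 / 2.101 = 7.14. t = 4 / 7.14 = 0.560, two-sided p = 0.582, against 0.581 printed. It reproduces within rounding.

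**2. What one time point can show.** In SD units the SE of a gap is sqrt(1/13 + 1/7) = 0.469. The smallest observed gap reaching p < 0.05 is 2.101 x 0.4688 = 0.985 SD. The StO2 interval implies an SD of 7.14 / 0.4688 = 15.2 points, so for StO2 that threshold is about 15 points.

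Power at one time point (noncentral t, 18 df):

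| True gap | Power | Missed |
|---|---|---|
| 0.8 SD | 0.365 | 63% |
| 1.0 SD | 0.523 | 48% |

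**3. Whether separate p values settle a change.** For two t statistics on the same subjects, the statistic for change is (t2 - t1) / sqrt(2(1 - rho)). This takes both gaps in the same direction.

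| Baseline p | Later p | p for change, rho 0.3 | rho 0.5 | rho 0.8 |
|---|---|---|---|---|
| 0.10 | 0.03 | 0.61 | 0.54 | 0.34 |
| 0.20 | 0.01 | 0.21 | 0.14 | 0.025 |

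The same pattern of non-significant then significant can go with no evidence of change or with some evidence of it. The answer depends on the within-subject correlation, which separate models do not use.

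**4. What a direct test would deliver.** SE(change in gap) = 0.469 x sqrt(2(1 - rho)); the 95% half-width is 2.101 times that. Power is for a gap that is 0 at baseline and 1.0 SD at the later time.

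| rho with baseline | 95% half-width (SD) | Power, unadjusted 0.05 | Power, first Holm step 0.05/15 |
|---|---|---|---|
| 0.8 | 0.62 | 89% | 51% |
| 0.7 | 0.76 | 74% | 31% |
| 0.5 | 0.98 | 52% | 15% |
| 0.3 | 1.17 | 40% | 9% |

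**The case against.** **A change can be read off what is planned.** Subtracting the planned means or the female coefficients gives a point estimate of the change in gap. That stands, so it would be wrong to say the plan offers no estimate at all. What is absent is any interval or test.

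**A real onset is plausible.** If the sentence means significance at all three later times, a constant gap seldom produces it. In simulations with a constant gap of 0.8 to 1.0 SD, one measure shows that pattern in about 3 to 5% of trials under equal correlations (0.5 to 0.8), and in about 8 to 13% if later times correlate 0.8 with each other but only 0.3 to 0.5 with baseline. All four measures show it together in at most about 0.5% and 2.7% respectively. This stands as a reason not to call the statement wrong. It rests on assumed gaps and correlations, and the documents do not confirm that every later test was significant. It does not replace an interval computed from data already held.

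**The sentence may be shorthand for the per-time tests.** The neighbouring skin-type summary is worded in terms of significance at each time. That reading is possible, and if it is what was meant, rewording is enough.

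**Similarity may rest on the baseline means and plots.** The baseline coefficients for the four measures are not printed, so a reader cannot infer that non-rejection was simply converted into similarity. The supportable statement is that similarity is not demonstrated.

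**The hypothesis of similar patterns.** A reader might count the conflict between that hypothesis and the conclusion as an error. It is not one, because data may contradict a hypothesis.

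**The equal-variance model fits the printed example only marginally.** The male interval (54 to 70) implies an SD of about 13.7 rather than 15.2. The ratio of half-widths is 15/8 = 1.88 where the model gives 1.69, and rounding allows no lower than 1.71. Results in SD units are therefore approximate.

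**Conclusion.** The concern holds in a limited form. The onset statement has no interval or test behind it in either document, and baseline similarity is not demonstrated. A reader might go further and conclude that no sex difference arose at inflation, or that a constant gap explains the results. The documents do not support either, since they print no post-baseline sex estimates and nothing for the four named measures.

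The size of the problem is the imprecision of 13 against 7: gaps up to about 0.98 SD go undetected at any one time point, and true gaps of 0.8 to 1.0 SD are missed about half to two-thirds of the time. These figures assume equal SDs; those for change also assume the correlation with baseline.

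Sex does not appear among the protocol's objectives (sections 1.1 to 1.3), and the device comparisons do not depend on this sentence. The skin-type conclusions make no onset claim and are not affected on this ground. Severity is minor to moderate.

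**What to change.** **Minimum.** Reword the closing sentence as sex differences at each time point, with estimates and 95% CIs. Replace the statement of baseline similarity by the baseline estimate and CI, and do not call it similarity unless the CI supports that. This changes wording only; the planned models already supply the numbers.

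**To keep an onset statement.** For each of the five SAP measures, fit one repeated-measures model over the four times with sex, time and sex x time (unstructured covariance, small-sample df). Report the change in the sex gap from baseline at occlusion, hyperaemia and recovery with 95% CIs. With complete data each contrast equals a two-sample t-test on change scores with 18 df. Apply Holm's adjustment over all 5 x 3 = 15 contrasts; restricting the family to the four measures named in the summary would select it from the results. Say that a difference started after baseline only if these contrasts support it, and report a non-significant contrast as inconclusive, not as proof of similar patterns.

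**Cost.** The models run on data already held. The downside is low precision: even a true 1.0 SD onset has only about 9 to 51% power at the first Holm step over the correlations assumed, so the statement may not survive even if it is true.
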